10 TABLES, FIGURES AND LISTINGS

10.1 List of tables

Table 1 – Protocol deviations summary overview

Table 2 – Demographics

Table 3 – Pericarditis History

Table 4 – Cardiovascular History

Table 5 – Other medical history by MedDRA System Organ Class

Table 6 – Other medical history by MedDRA Preferred Term

Table 7 – Baseline medication by WHO Anatomical Therapeutic Chemical (ATC) Classification

Table 8 – Anthropometric assessment and vital signs at baseline – Descriptive statistics

Table 9 – Physical examination at baseline – Descriptive statistics

Table 10 –Questionnaire at baseline: NRS and C-SSRS – Descriptive statistics

Table 11 – Standard 12-lead Electrocardiogram (ECG) at baseline – Descriptive statistics

Table 12 –Laboratory tests results at baseline – Descriptive statistics

Table 13 –Laboratory tests results at baseline – Descriptive statistics by gender

Table 14 –Laboratory tests results at baseline below, within and above the normal range

Table 15 – Study drug exposure

Primary efficacy endpoint

Table 16 – Primary endpoint – Worst 11-point NRS score at Week 8 and 11-point NRS change from baseline to Week 8 – Descriptive statistics

Additional efficacy endpoints

Table 17 – Worst 11-point NRS score and change from baseline by week up to 26 weeks – Descriptive statistics

Table 18 – Patients with normalized CRP levels (i.e with a CRP \leq 0.5 mg/dL) at 8 weeks and 26 weeks (for patients with CRP \geq 1.0 mg/dL at baseline)

Table 19 – Time to CRP normalization (in weeks) for patients with CRP \geq 1.0 mg/dL at baseline

Table 20 – CRP change from baseline at 26 weeks – Descriptive statistics

Table 21 – Patients with pericarditis recurrence during the extension period (EP),

Further exploratory endpoints

Table 22 – Worst 11-point NRS score and change from baseline by week up to 26 weeks for patients enrolled with qualifying CRP ≥ 1.0 mg/dL – Descriptive statistics

Table 23 – Worst 11-point NRS score and change from baseline by week up to 26 weeks for patients for patients who qualified for the trial on basis of past CMR findings and had qualifying CRP < 1.0 mg/dL – Descriptive statistics

Safety related

Table 24 – Overview of reported adverse events

Table 25 – Non-serious adverse events by MedDRA System Organ Class

Table 26 – Non-serious adverse events by MedDRA Preferred Term

Table 27 – Serious adverse events by MedDRA System Organ Class

Table 28 – Serious adverse events by MedDRA Preferred Term

Table 29 – Patients with a worsening of C-SSRS ideation and behaviour scores compared to baseline

Table 30 – Laboratory tests results (absolute and change from baseline) during the 26-week study period – Descriptive statistics

Table 31 – Patients who experience changes in laboratory parameters during the 26-week study period

Table 32 – ECG intervals (absolute and change from baseline) during the 26-week study period – Descriptive statistics

Table 33 – Vital signs (absolute and change from baseline) during the 26-week study period – Descriptive statistics

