### **9.2.11    Management of AEs**

#### ***9.2.11.1   AE Reporting***

An AE is defined as any new untoward medical occurrence or worsening of a pre-existing medical condition in a patient or clinical investigation patient administered an investigational (medicinal) product and that does not necessarily have a causal relationship with this treatment. An AE can therefore be any unfavorable and unintended sign (including an abnormal laboratory finding, for example), symptom, or disease temporally associated with the use of investigational product, whether or not considered related to the investigational product.

AEs can be spontaneously reported or elicited during open-ended questioning, examination, or evaluation of a patient. (In order to prevent reporting bias, patients should not be questioned regarding the specific occurrence of one or more AEs.)

Any AE that results in any of the following outcomes will be considered an SAE:

1. Death

2. Life-threatening situation (patient was at risk of death at the time of the event. This does not refer to an event that might have caused death if it was of greater intensity.)
3. New in-patient hospitalization or prolongation of existing index hospitalization
4. Persistent or significant disability or incapacity
5. Congenital anomaly or birth defect
6. QTc interval increases to > 500 msec or >60 msec from baseline.
7. Important medical events that may not result in death, be life-threatening, or require hospitalization but may jeopardize the patient and may require medical or surgical intervention to prevent one of the above outcomes (based upon appropriate medical judgment), e.g., allergic bronchospasm requiring intensive treatment in an emergency room or at home, blood dyscrasias or convulsions that do not result in in-patient hospitalization, or the development of drug dependency or drug abuse. Potential Drug-Induced Liver Injury (DILI) is also considered an important medical event. (See Section 9.2.11.3 for the definition of potential DILI.)

All SAEs experienced by a patient after informed consent has been obtained must be reported to SOCAR Research (SOCAR) within 24 hours of the site's awareness of the event.

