2.3.4 Safety endpoints

Per section 4.2.2 of the study protocol (Amendment #2), the safety outcomes will encompass the following:

- Occurrence of adverse / serious adverse events as of the start of the IMP through the last study visit.

- Change (from baseline) in C-SSRS at the end of patient follow-up – i.e. either at week 8 or week 26-week study visit.
- Change (from baseline) in laboratory parameters, including liver function parameters and INR at the end of patient follow-up – i.e. either at the week 8 or the week 26 study visit.
- Change (from baseline) in ECG intervals/findings parameters at the end of patient follow-up – i.e. either at the week 8 or the week 26-week study visit.

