8 STATISTICAL ANALYSES

The complete set of tables, figures and listings planned to be generated by this SAP is displayed in section 10.

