8.6.1 Adverse events (AEs)

The number of adverse events and percentage of patients with at least one adverse event will be summarized by system organ class and by preferred terms (MedDRA).

AEs will be considered as treatment - emergent adverse events (TEAE) if the event onset time (and date) is $>$ start of the IMP. Adverse events with incomplete onset dates will be summarized as TEAE regardless of severity and relationship to the IMP.

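### The SAP promises all adverse events by system organ class and preferred term, but its complete table list has no such table and no title says whether it is limited to treatment-emergent events

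*SAP*

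**What the plan says.** SAP 8.6.1 sets out the adverse event summary. Besides event counts, the "percentage of patients with at least one adverse event will be summarized by system organ class and by preferred terms (MedDRA" dictionary). It makes no distinction by seriousness, and serious events have their own paragraph in 8.6.2. The natural reading is that 8.6.1 covers all adverse events.

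The same section defines treatment emergence. It begins "AEs will be considered as treatment - emergent adverse events (TEAE) if the event onset time (and date) is" and goes on to require onset after the start of study drug. It adds: "Adverse events with incomplete onset dates will be summarized as TEAE regardless of severity and relationship to the IMP". SAP 9.5.1 supplies rules for partial onset dates, anchored to the date of first dose.

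SAP 8 says of the outputs: "The complete set of tables, figures and listings planned to be generated by this SAP is displayed in section 10". In 10.1 the adverse event tables are an overview (24), non-serious events by SOC (25) and by PT (26, listed as "Table 26 – Non-serious adverse events by MedDRA Preferred Term"), and serious events by SOC (27) and by PT (28). Listing 5 in 10.3 shows serious and non-serious events together at patient level.

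SAP 2.3.4 words the safety endpoint as "Occurrence of adverse / serious adverse events as of the start of the IMP through the last study visit". Protocol 9.1 (Visit 1) and footnote 5 of Protocol 17.2 start adverse event recording at informed consent.

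**The concern.** Two things described in the SAP text do not reach the outputs. The first is the summary of all events by SOC and PT. The second is the treatment-emergent restriction, which is defined but appears in no table title. A programmer who works from section 10 is told neither to build the combined table nor to apply the filter.

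This matters because the usual safety question in a pilot of about 25 patients is how many of them had a given event on drug. Patient percentages from a serious table and a non-serious table cannot be added, because a patient with both kinds of event under one term is counted in each.

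Terms that fall in both tables are foreseeable here, because the protocol makes seriousness depend partly on the size of a finding. One seriousness criterion is "QTc interval increases to > 500 msec or >60 msec from baseline", while Protocol 9.2.3 lets other new clinically relevant ECG changes be reported as either an AE or an SAE. Potential drug-induced liver injury must be an SAE (Protocol 9.2.11.3), while an abnormal laboratory finding can be an ordinary AE (9.2.11.1).

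**Working it through.** **Step 1: promise against output.** No figure in the plan can be reproduced here, so the check sets the text beside the table list.

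| Output | All AEs together | By SOC or PT | Title says treatment-emergent |
|---|---|---|---|
| Table 24 | Overview; content not specified | Not in title | No |
| Tables 25, 26 | Non-serious only | Yes | No |
| Tables 27, 28 | Serious only | Yes | No |
| Listing 5 | Yes, patient level | Not a summary | No |

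Of the five tables, none is titled as giving all events by SOC or PT, and none is titled as treatment-emergent.

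**Step 2: what can be recovered from the separate tables.** For one preferred term, let a be the number of patients in Table 26, b the number in Table 28, and N the number of patients treated. The number with the term at all is the size of a union:

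max(a, b) ≤ patients with the term ≤ min(N, a + b)

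Take N = 25, the approximate enrolment in Protocol 11.1. One patient is then 1/25 = 4 percentage points. The documents give no event rates, so the counts below are assumptions used only to show the range.

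| a (non-serious) | b (serious) | Patients with the term | Incidence |
|---|---|---|---|
| 3 | 0 | 3 | 12%, exact |
| 3 | 1 | 3 to 4 | 12% to 16% |
| 4 | 2 | 4 to 6 | 16% to 24% |
| 6 | 3 | 6 to 9 | 24% to 36% |
| 10 | 5 | 10 to 15 | 40% to 60% |

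While a + b ≤ N, the width of the range is min(a, b)/N. It is zero when a term occurs in one class only, and 4 points when there is a single serious case. Event counts, as distinct from patient counts, do add across the two tables.

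**Step 3: the SOC level.** The same bound applies to Tables 25 and 27, where overlap needs less coincidence. A patient with one serious and one non-serious event in the same SOC is counted in both tables even if the preferred terms differ.

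**Step 4: the treatment-emergent window.** Events enter the database from consent, and the endpoint in SAP 2.3.4 starts at first dose. SAP 8.6.1 and 9.5.1 provide what is needed to separate the two periods. Tables 24 to 28 do not say that the separation is made.

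**The case against.** The strongest reply is that the practical loss is small. A term reported only as non-serious can be read exactly from Table 26, and one reported only as serious from Table 28. With one serious case the doubt is at most one patient. Listing 5 allows a hand count, which is manageable with about 25 patients. QTc and liver values are also reported directly in Tables 30 to 32. The study is descriptive, and nothing inferential hangs on these counts. All of this stands, and it limits the size of the point. It does not supply the summary that 8.6.1 promises, because a listing is not that summary and the laboratory and ECG tables do not count adverse events.

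A reader might infer that incidence cannot be read for any term. The documents do not support that: the gap is confined to terms and classes with both serious and non-serious cases.

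A reader might also infer that pre-dose events are mixed into the tables. That is not established either. SAP 2.3.4 points to a window that opens at first dose, and the definition in 8.6.1 and the imputation rules in 9.5.1 fit that intent. No table shells are available to show what Table 24 or the others contain. The pre-dose period may also be short. Protocol 9.1 sets no limit between consent and treatment assignment, but it places consent within Visit 1, scheduled within 72 hours of Day 1, and SAP 4.3 puts the first dose on the evening of the screening visit. What can be said is that the titles leave the restriction unstated.

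**Conclusion.** The point holds as a mismatch between the SAP's text and its own table list. The summary of all events by SOC and PT in 8.6.1 has no table, and the treatment-emergent definition is not carried into any title in Tables 24 to 28.

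The consequence is that the once-per-patient incidence is not tabulated for any term or SOC with both serious and non-serious cases. For these, the listed outputs give only the range max(a,b) to a+b, at about 4 percentage points per patient. How often this happens depends on data the documents do not contain, so the ranges shown are illustrations and not predictions.

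The conclusion assumes that the table titles describe the content and that section 10 is complete, as SAP 8 states. It is worth correcting because safety is a stated objective and adverse event counts head the safety parameters in Protocol 4.2.2.

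**What to change.** In SAP 10.1:

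- Add two tables, *All treatment-emergent adverse events by SOC* and *All treatment-emergent adverse events by PT*. Count each patient once per SOC or term, with serious and non-serious events together, and show the number of events alongside.
- Keep Tables 25 to 28 as the non-serious and serious subsets. They need not be removed.
- Apply the treatment-emergent definition of 8.6.1 to Tables 24 to 28 and state it in their titles.
- Show any event with onset between consent and first dose only in Listing 5.

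The cost is two extra tables, one filter and some title edits. No new data are needed and the protocol does not change.

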10.2 List of figures

Figure 1 – Consort

Figure 2 – Worst NRS score by week – mean (SD)

Figure 3 – Laboratory test results by week – mean (SD) – Graphical representation for each parameter

Figure 4 – Laboratory test results by week – mean change from baseline (SD) – Graphical representation for each parameter

Figure 5 – Patients who experience changes in laboratory parameters during the course of the study – bar chart over time (for each parameter)

10.3 List of listings

Listing 1 – Patient disposition: Informed consent signature date, date of enrolment, death date, premature withdrawal from follow-up, premature withdrawal from study treatment

Listing 2 – Demographics and Baseline Characteristics

Listing 3 – ECG abnormalities considered clinically significant reported at enrolment

Listing 4 – Prior, baseline and concomitant medications

Listing 5 – Serious and non-serious adverse events reported during study

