#### 4.2.2 Safety Parameters

Safety parameters include the number of AEs and SAEs, changes in C-SSRS as well as changes in laboratory parameters, including liver function parameters and INR as well as ECG intervals and rhythm during the 26-week study period.

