### 6.3 *Follow-up Procedures*

At every assessment before study drug dose increase the patient will be re-evaluated. This includes ECG monitoring at approximately 5 hours post-morning dose ( $T_{max}$ ) to surveil for deleterious effects on ECG intervals (particularly the QTc interval) and rhythm.

Drug titration will be dependent on investigator or designate interrogation of the ECGs and the absence of abnormalities on those ECGs.

Vital signs, blood chemistry including liver function tests, hematology as well as INR assessments will be carried out at selected visits. Concurrent medications and (S)AEs will be recorded at all visits.

Final efficacy assessments will take place after 26 weeks of study treatment and include a clinical assessment, vital signs, Pain score NRS, a 12-lead ECG, the C-SSRS, as well as laboratory assessments.

For patients who do not enter the EP, final assessments will be done after 8 weeks, i.e. at Visit 5.

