### **9.2.3 Standard 12-lead Electrocardiogram (ECG)**

A 12-lead ECG will be performed at baseline, and at all in-person follow-up visits. Visits 2 (Day 3), 3 (Day 10) and 4 (Week 3) can only be virtual if an ECG can be performed and transmitted to the site for review.

The ECG after start of study medication will be recorded approximately 5 hours (time window 3.5 – 6 hours) post-morning dose ( $T_{max}$ ) to surveil for deleterious effects on ECG intervals (particularly the QTc interval) and rhythm. Continuation on study drug will be assessed by the investigator or designate dependent on interrogation of the ECG, most importantly the QT interval.

The QT interval can be obtained from the automated measurements of the ECG recorder unless the data quality is poor. In this case, the QT interval is measured from the beginning of the QRS complex to the end of the T wave and averaged over three cardiac cycles. The average QT interval should be corrected for heart rate variability using Bazett's formula ( $QT_c = QT / \sqrt{RR}$ ) or Fridericia's formula ( $QT_c = QT / RR^{1/3}$ ) to create the QTc interval. Each patient should have the QTc measured using the same method on all designated days in the study.

The presence of a bundle branch block (BBB) represents a particular challenge in properly measuring the QTc interval. Following international recommendations, QT interval should be measured in leads showing the longest QT interval, which is usually in right precordial leads. In presence of a BBB, these leads are strongest affected by conduction delay and therefore hamper adequate measurement. A new formula for evaluation of the QT interval in patients with left bundle branch block (LBBB) was introduced in 2014:

$$QT_{mean} = QT_{BBB} - 50\% QRS_{BBB} \text{ (Bogossian et al. 2014)}$$

This formula has proved to be a reliable tool in clinical practice for QTc interval evaluation in patients with LBBB, right bundle branch block (RBBB) or bifascicular block. (Bogossian et al. 2020; Erkacic et al. 2020)

Similarly, ventricular paced rhythm with an increased QRS duration can impact the QT interval. In patients with ventricular paced rhythm, 50ms should be subtracted from the Bazett's formula or Fridericia's formula.(Chakravarty et al. 2015)

If the QTc interval increases to 500 msec or more – or increases 60 msec or more from the baseline recording on any one measurement, this must be reported as an SAE and the study medication must be discontinued.

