8.6.5 ECG parameters

Descriptive statistics of absolute value and change from baseline of ECG intervals and rhythm during the 26-week study period.

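### The SAP promises on-treatment ECG rhythm but plans no output for it, and no planned output counts patients who reach the protocol's QTc limits

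*SAP*

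**What the plan says.** Protocol 4.2.2 includes "ECG intervals and rhythm during the 26-week study period" among the safety parameters. Protocol 6.3 says the ECGs near peak exposure are taken "to surveil for deleterious effects on ECG intervals (particularly the QTc interval) and rhythm". SAP 2.3.4 carries this over as a safety endpoint: change from baseline in ECG intervals and findings at the end of a patient's follow-up. SAP 8.6.5 then commits to "Descriptive statistics of absolute value and change from baseline of ECG intervals and rhythm during the 26-week study period".

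On outputs, SAP section 8 states: "The complete set of tables, figures and listings planned to be generated by this SAP is displayed in section 10". In that list:

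- Table 32 is the only post-baseline ECG table. Its subject is "ECG intervals (absolute and change from baseline) during the 26-week study period".
- Listing 3 covers "ECG abnormalities considered clinically significant reported at enrolment". It belongs to SAP 8.3.9, a baseline section, which is also the only place where abnormal ECGs are tabulated.
- None of Figures 1 to 5 concerns the ECG.

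Protocol 9.2.3 sets individual QTc limits. "If the QTc interval increases to 500 msec or more", or rises by at least 60 msec over baseline, "this must be reported as an SAE and the study medication must be discontinued". Other new ECG changes that are clinically relevant must also be reported, as an AE or SAE.

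**The concern.** A safety parameter named in the protocol and repeated in two SAP sections loses half its content in the output list. If the programmers follow section 10, no table or listing will be dedicated to rhythm or ECG abnormalities after the first dose.

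The QTc limits apply to individual patients, yet the ECG data are to be summarized only as distributions. Other safety data are treated differently: the C-SSRS has a table of patients who worsen (Table 29), and laboratory data have a table and a bar chart of patients whose results change (Table 31 and Figure 5). The ECG has no equivalent. At stake is whether the clinical study report can state, from the ECG data, how many patients had a new rhythm or abnormality finding on drug and how many reached a QTc limit.

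**Working it through.** The plan gives no figure to reproduce. The check sets the promised content against the outputs and then asks what the remaining routes can show.

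**1. Promise against output**

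| ECG item | Promised on treatment | Baseline output | Dedicated on-treatment output |
|---|---|---|---|
| Intervals (PR, QRS, QT, QTc) | Protocol 4.2.2, SAP 2.3.4, SAP 8.6.5 | Table 11 | Table 32 |
| Rhythm | Protocol 4.2.2, SAP 8.6.5 | none named | none |
| Findings or abnormalities | SAP 2.3.4 | SAP 8.3.9, Listing 3 | none |
| Patients reaching a QTc limit | limits set in Protocol 9.2.3, no count promised | not applicable | none |

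Rows two and three are inconsistencies within the SAP. Row four is an omission and contradicts no promise.

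**2. Volume of data affected.** The schedule in SAP 4.5 for protocol amendment 2 has ECGs after the first dose at Visits 2, 3, 4, 5, 7 and 9, so six per patient who completes the extension. With about 25 patients, 6 × 25 = 150 readings at most. The six patients enrolled under amendment 1 had different visit timing, and patients who stop at Week 8 contribute fewer.

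**3. What Table 32 can show.** SAP 9.1 defines the summary of a continuous variable as count, mean, SD, median, interquartile range, minimum and maximum. Suppose k of 25 patients rise by 60 msec at one visit and the others do not change. Then mean = 60k/25 and SD = 60 × √[k(25 − k)/(25 × 24)].

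| k | Mean change (msec) | SD (msec) | Maximum (msec) |
|---|---|---|---|
| 1 | 2.4 | 12.0 | +60 |
| 2 | 4.8 | 16.6 | +60 |
| 3 | 7.2 | 19.9 | +60 |

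The maximum shows that someone reached the limit but not how many did. With real spread in the other patients, the number cannot be recovered from the mean and SD. A maximum at each visit also does not say whether the same patient is responsible each time.

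**4. How often the count would add to the maximum.** It adds information when two or more patients reach a limit. The documents give no rate, so p is assumed. With n = 25, P(at least 1) = 1 − (1 − p)^25 and P(at least 2) = 1 − (1 − p)^25 − 25p(1 − p)^24.

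| Assumed p | P(at least 1) | P(at least 2) |
|---|---|---|
| 2% | 0.397 | 0.089 |
| 4% | 0.640 | 0.264 |
| 8% | 0.876 | 0.605 |
| 12% | 0.959 | 0.820 |

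**5. What the AE and SAE route can show.** Events at the limits, and other clinically relevant ECG changes, should reach Tables 24 to 28 and Listing 5. Three things stop that route from being a clean count:

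- *Limits.* Protocol 9.2.3 includes values equal to 500 msec or to a 60 msec rise. The SAE definition in Protocol 9.2.11.1 uses strict inequalities. A patient exactly at a limit is an SAE under one section and not under the other.
- *Formula.* Protocol 9.2.3 allows Bazett (QT/RR^(1/2)) or Fridericia (QT/RR^(1/3)), kept constant within a patient. Their ratio is RR^(−1/6), so Bazett gives the higher value whenever RR is below 1 second. SAP 8.3.9 names Fridericia only. A site's SAE report and the analysed QTc can disagree, and no planned output would reveal it.
- *Judgement.* A rhythm finding that the site does not consider clinically relevant generates no AE and so appears nowhere.

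**The case against.** The strongest reply is that the plan already catches the patients who matter. Table 32 is not limited to means: its maximum would show a +60 msec change. Anyone at a QTc limit is a mandatory SAE and must stop the drug, so should appear in Tables 24, 27 and 28, in Listing 5, and in Listing 1 as withdrawn from study treatment. Clinically relevant rhythm changes reach the AE tables. Conduction is covered in Table 32 through PR and QRS. Listing 3 is consistent with its parent section, which is about baseline. This is also a descriptive pilot of about 25 patients, for which finer QTc bands such as 450, 480 or 30 msec are convention and are not set in either document as QTc safety limits.

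Most of that stands, and it rules out stronger readings. A reader might infer that QTc outliers go unsummarized, or that the ECG part of the safety objective cannot be answered. The SAE route and the Table 32 extremes contradict both. A reader might also infer that QTc is the trial's main safety concern. Protocol 6.3 and 9.2.3 single it out among ECG effects, but nothing ranks it above liver injury, which has its own SAE and discontinuation criteria in Protocol 9.2.11.3. The two-patient line in the table above illustrates what a maximum can show; those patients would not be lost.

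The reply does not supply an on-treatment rhythm output, which the SAP itself promises. Nor does it turn site-reported events, under two correction formulas and two statements of the limits, into a count derived from the ECG data.

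**Conclusion.** The point holds as an inconsistency between SAP 2.3.4 and 8.6.5 on one side and section 10 on the other. Rhythm and ECG findings on treatment are promised and have no dedicated output. In addition, no planned output counts patients at the protocol's QTc limits. Both reach the report only through AE and SAE reporting and, for QTc, the extremes in Table 32.

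The practical size is moderate. Clinically relevant events should still be visible. What would be missing is the patient-level picture across up to about 150 on-treatment ECGs, including rhythm findings not judged clinically relevant, and a check of SAE reports against the recorded QTc. This conclusion assumes that section 10 is followed as the complete list. The probabilities above rest on assumed rates and show only when a count would add to a maximum.

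**What to change.** 1. Extend Listing 3 from enrolment to all visits.
2. Add one on-treatment ECG table to SAP 10.1 and describe it in SAP 8.6.5. It should give (a) a shift from baseline to worst on-treatment ECG abnormality status, with rhythm, as captured in the eCRF, and (b) n (%) of patients whose highest on-treatment QTc reaches the protocol's 500 msec limit, and n (%) whose largest increase from baseline reaches its 60 msec limit.
3. State one formula for these counts. Fridericia matches SAP 8.3.9. Apply the corrections in Protocol 9.2.3 for bundle branch block, bifascicular block and paced rhythm, so that those patients are not misclassified.
4. Before the counts are defined, Protocol 9.2.3 and 9.2.11.1 must be reconciled on whether values exactly at the limits are included.
5. Lower descriptive cut-points (450, 480 or 30 msec) are optional and are the sponsor's choice.

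The cost is one extra table and a wider listing. This assumes that follow-up ECG readings, including rhythm and abnormality status, are recorded in the eCRF. The documents do not show that form, so this should be confirmed first. If only intervals are recorded after baseline, the QTc counts remain feasible, but SAP 8.6.5 should then say that rhythm is covered through AE reporting alone.
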